Appendix 3 Concomitant Medications (Including Foods and Herbal Products) (cont.)

Class	Expected Interaction	Recommendation	Examples of Drugs in this Class ^a
Sensitive and narrow therapeutic window CYP3A substrates	Potential for increased plasma concentrations of CYP3A substrates due to inhibition of metabolism by GDC-0853	Use with caution and monitor for adverse events related to CYP3A substrates as directed by product labeling	 Antiemetic/prokinetic (aprepitant, cisapride) Anti-histamine (astemizole, terfenadine) Anti-hypertensive/cardiac (dronedarone, eplerenone, felodipine, nisoldipine, quinidine, ticagrelor, vardenafil) Benzodiazepines (alprazolam, diazepam, midazolam) Lipid-lowering (simvastatin, lovastatin) Migraine (eletriptan, ergotamine) Steroids (budesonide, fluticasone) Other (alfentanil, buspirone, conivaptan, darifenacin, dasatinib, dihydroergotamine, fentanyl, lurasidone, pimozide, quetiapine, sildenafil, tolvaptan, triazolam)

^a The following list is not comprehensive. Please refer to the following Web sites for additional information and consult the Medical Monitor if necessary:

U.S. FDA Table of Substrates, Inhibitors, and Inducers (http://www.fda.gov/Drugs/DevelopmentApprovalProcess/DevelopmentResources/DrugInteractionsLabeling/ucm093664.htm); Indiana University Department of Medicine P450 Interaction Table (http://medicine.iupui.edu/clinpharm/ddis).

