4.3.1.3 Acid-Reducing Agents

Patients who use antacids (e.g., Maalox[®], Pepto-Bismol[®], Rolaids[®]) for symptomatic relief of heartburn should take GDC-0853 at least 2 hours before or 2 hours after antacid administration because GDC-0853 requires an acidic gastric environment in order to be absorbed.

Patients may be treated with PPIs or H2RAs, but should remain on a stable regimen throughout the study.

At visits with scheduled PK assessments (see Appendix 1), any use of PPIs, H2RAs, and/or *other* antacids (*e.g.*, *Maalox*®, *Pepto-Bismol*®, *Rolaids*®) should be recorded as concomitant medications, including the date and time of last administration.

4.3.2 **Prohibited Therapy**

A listing of concomitant medications that is prohibited or should be used with caution because of potential drug-drug interactions is provided in Appendix 3.

Intravenous, intra-articular, or intramuscular corticosteroids; biologic response modifiers; tofacitinib or other JAK inhibitors; and medications listed below are not allowed during this study and any use will require discontinuation of GDC-0853.

Use of the following therapies is prohibited during the study, unless otherwise specified below:

- Investigational therapy other than study drug
- Abatacept
- Adalimumab
- Anakinra
- Anti-TNF inhibitors (infliximab, etanercept, golimumab, certolizumab, or biosimilar equivalents)
- Chlorambucil
- Cyclophosphamide
- Cyclosporine
- Immunosorbent column
- Intravenous or intramuscular steroids
- Mycophenolate mofetil
- Mycophenolic acid sodium
- Oral anticoagulants, including but not limited to warfarin, dabigatran, rivaroxaban, apixaban
- Anti-platelet agents, e.g. clopidogrel (Note: NSAIDs and low-dose aspirin are acceptable.)
- Heparin, LMWH
- Penicillamine
- Rituximab (or biosimilar equivalent)
- Sirolimus
- Tacrolimus

- Tocilizumab and other anti-IL6R or anti-IL6 agents
- Tofacitinib and other JAK inhibitors
- All biosimilar agents

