In vitro data suggest that GDC-0853 is metabolized by CYP3A, and there is a moderate to high potential for a drug-drug interaction with any medication that strongly inhibits or induces this enzyme. Therefore, medications in the following categories (listed in detail in Appendix 3) should be avoided for 7 days or 5 half-lives, whichever is longer, prior to the first dose of study drug until the last dose of study drug. If use of one of these medications is necessary, the risks and benefits should be discussed with the Medical Monitor prior to concomitant administration with study drug.

- Moderate or strong CYP3A inhibitors
- Moderate or strong CYP3A inducers

Data also suggest that GDC-0853 inhibits CYP3A, and there is a moderate to high potential for a drug-drug interaction with any medication that is metabolized by CYP3A. Plasma concentrations of the medications in the following categories (listed in detail in Appendix 3) may increase; therefore, they should be used with caution:

- Sensitive CYP3A substrates
- CYP3A substrates with a narrow therapeutic index

The medications listed above and in Appendix 3 are not necessarily comprehensive. Thus, the investigator should consult the prescribing information for any concomitant medication as well as the Internet references provided below when determining whether a certain medication is metabolized by or strongly inhibits or induces CYP3A. The investigator should contact the Medical Monitor if questions arise regarding medications not listed above.

http://www.fda.gov/downloads/Drugs/GuidanceComplianceRegulatoryInformation/Guidances/UCM292362.pdf

http://medicine.iupui.edu/clinpharm/ddis/table.aspx

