4.5.2 Study Treatment Discontinuation

Patients must discontinue study treatment if they experience any of the following:

- Pregnancy
- Anaphylaxis or other severe hypersensitivity reaction

- Malignancy (with the exception of non-serious local and resectable basal or squamous cell carcinoma of the skin)
- Any serious infection or infection requiring treatment with an IV antimicrobial agent
- Any prohibited medication as defined in Section 4.3
- Any Grade 3 or greater thrombocytopenia (National Cancer Institute Common Terminology Criteria for Adverse Events [NCI CTCAE v4.0])
- Any Grade 4 neutropenia (NCI CTCAE v4.0)
- Failure to achieve a 20% improvement in both SJC and TJC (relative to baseline values in Study GA29350) at Week 24

Patients who discontinue study treatment prematurely for the reasons listed above will be asked to return to the clinic for an early termination visit (see Section 4.5.1) followed by 8 weeks of safety follow-up.

The primary reason for study treatment discontinuation should be documented on the appropriate eCRF. Patients who discontinue study treatment prematurely will not be replaced.

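### Appendix 3 lists ticagrelor, an anti-platelet agent, as usable with caution, while Section 4.3.2 bans anti-platelet agents and requires GDC-0853 to be stopped; no text says which rule prevails

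*Combined protocol and SAP*

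**What the plan says.** Four parts of the protocol bear on ticagrelor.

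- **Section 4.3.2 (Prohibited Therapy)** lists "Anti-platelet agents, e.g. clopidogrel (Note: NSAIDs and low-dose aspirin are acceptable" among the banned treatments. Clopidogrel is only an example; the ban is on the class, and the note gives the only exemptions. On consequences, the section says that "medications listed below are not allowed during this study and any use will require discontinuation of GDC-0853". The list is introduced with "Use of the following therapies is prohibited during the study, unless otherwise specified below". The section also opens with a cross-reference: "A listing of concomitant medications that is prohibited or should be used with caution because of potential drug-drug interactions is provided in Appendix 3".
- **Section 4.5.2 (Study Treatment Discontinuation)** includes among the mandatory stopping reasons "Any prohibited medication as defined in Section 4.3".
- **Section 4.3.2.2 (CYP3A Inhibition)** says of sensitive and narrow-therapeutic-index CYP3A substrates: "Plasma concentrations of the medications in the following categories (listed in detail in Appendix 3) may increase; therefore, they should be used with caution".
- **Appendix 3**, in its row for those substrates, names "Anti-hypertensive/cardiac (dronedarone, eplerenone, felodipine, nisoldipine, quinidine, ticagrelor, vardenafil" and recommends "Use with caution and monitor for adverse events related to CYP3A substrates as directed by product labeling".

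The row carries no note that ticagrelor is banned on other grounds.

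**The concern.** A site whose patient is prescribed ticagrelor during the extension would reasonably look the drug up by name. The only place it appears is Appendix 3, where the instruction is caution, not avoidance. It is filed there as a cardiac drug, so nothing prompts the reader to connect it with the anti-platelet ban, where clopidogrel is the only agent named.

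What is at stake is a bleeding safeguard. Section 5.1.1.3 says it is not known whether GDC-0853 raises bleeding risk and singles out patients on anti-platelet or anticoagulant therapy. Section 1.3 reports two oncology patients with gastrointestinal bleeding of Grade 3 or higher while on NSAIDs or acetylsalicylic acid. Section 5.2.3 makes bleeding of Grade 2 or above an event of special interest. The Appendix 3 row also expects GDC-0853 to inhibit the metabolism of the drugs it names, so a patient managed by that row could receive an anti-platelet agent at increased exposure.

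**Working it through.** The check is mainly textual. The only arithmetic is a count.

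**1. Is ticagrelor within the ban?** The documents do not state its class; Appendix 3 groups it with anti-hypertensive and cardiac drugs. That it is an anti-platelet agent is settled pharmacology and needs no outside study or figure. It is neither an NSAID nor aspirin, so neither exemption in Section 4.3.2 applies. It is therefore banned, and Sections 4.3.2 and 4.5.2 both require GDC-0853 to be stopped if it is used.

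**2. Does Appendix 3 read as permission?** The rows of Appendix 3 carry different instructions. For CYP3A inhibitors and inducers the instruction is to avoid them before and during treatment. For the substrate row it is caution with monitoring. A reader comparing the rows will take the second as allowing use. Section 4.3.2.2 repeats the caution instruction for the category and makes no exception for anti-platelet agents.

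**3. Does any text rank the two?** None was found.

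- The cross-reference in Section 4.3.2 presents Appendix 3 as covering both prohibited drugs and drugs to be used with caution, and gives no order.
- The Appendix 3 footnote suggests consulting the Medical Monitor if needed, which is not a precedence rule.
- The exception phrase introducing the Section 4.3.2 list names neither ticagrelor nor Appendix 3.

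**4. Can a site assume the stricter text always wins?** Not safely, because the protocol contains a counter-example. The opening of Section 4.3.2 puts intra-articular corticosteroids among the treatments that require GDC-0853 to be discontinued. Section 4.3.1.1.4 allows up to 3 such injections from Week 12, and Section 4.4.5.1.1 explains how to score an injected joint. There the permissive text is evidently the intended one.

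**5. How much of the row is affected?** Drugs named in the substrate row of Appendix 3, by group:

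| Group | Drugs named |
|---|---|
| Antiemetic/prokinetic | 2 |
| Anti-histamine | 2 |
| Anti-hypertensive/cardiac | 7 |
| Benzodiazepines | 3 |
| Lipid-lowering | 2 |
| Migraine | 2 |
| Steroids | 2 |
| Other | 13 |
| **Total** | **33** |

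2 + 2 + 7 + 3 + 2 + 2 + 2 + 13 = 33, of which ticagrelor is 1. The count shows how local the slip is; it does not measure risk.

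**6. Who could be affected?** Section 4.1.2 excludes patients who took anti-platelet agents during Study GA29350 or after its last dose. That leaves only patients who first start ticagrelor during the 52-week extension.

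**7. Does any analysis change?** No. Section 6 plans no statistical tests, and a patient who stops GDC-0853 remains in the intent-to-treat efficacy population of Section 6.5.

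**The case against.** The best reply is that the two texts can be followed together. Advice to use a drug with caution is a condition on use and does not license a drug banned for another reason. Section 4.3.2 already limits Appendix 3 to drug-drug interactions, whereas the anti-platelet ban concerns bleeding, and a site that applies the ban breaches nothing in the appendix. The exception phrase introducing the list is most naturally read as pointing to the note on NSAIDs and aspirin beside the anti-platelet entry. Other protections exist: the class exclusion at entry, recording of all concomitant medication, reporting of Grade 2 or higher bleeding within 24 hours, and withholding of GDC-0853 for bleeding of Grade 3 or above.

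Much of this stands. A careful site would reach the right answer, reading the exception phrase as an override is strained, and few patients are likely to be involved. It does not remove the problem. Sites are sent to a table that names the drug and gives the weaker instruction, and the intra-articular steroid text shows that Section 4.3.2 cannot be assumed to prevail whenever another section is more permissive. The reporting and withholding rules act only after a bleed; the ban is meant to act before one.

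**Conclusion.** The concern holds. For one named drug, an operative table gives an instruction weaker than the protocol's own prohibition, and nothing states which governs. It is a patient-safety wording inconsistency that should be corrected, although it is unlikely to arise often: it needs a new ticagrelor start during the extension and a site that relies on Appendix 3 alone. The documents give no figure for how often that would happen, so no rate can be offered. No estimate, analysis population or planned summary is altered. The conclusion rests on one premise from outside the documents, ticagrelor's drug class, which is not in dispute.

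**What to change.** In Appendix 3, either delete ticagrelor from the substrate row or annotate it as prohibited with a pointer to Section 4.3.2. Add one sentence, in Section 4.3.2 or at the head of Appendix 3, stating that the appendix deals with drug-drug interactions and does not override the prohibitions in Section 4.3.2. Do not create an exception for ticagrelor; the ban should stay as it is.

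The cost is one table entry and one sentence. Data collection and analysis are unchanged.

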Appendix 4 Childbearing Potential, Pregnancy Testing, and Contraception

For Women

All women of childbearing potential (including those who have had a tubal ligation) will have a urine pregnancy test on Study Day 1 prior to administration of study drug and at monthly intervals throughout the study. If a urine pregnancy test result is positive, study drug will not be administered until pregnancy is ruled out. The result must be confirmed by a serum pregnancy test (conducted by the local laboratory). Refer to Section 5.4.3 of the protocol for management of a patient with a confirmed pregnancy.

All female patients are considered to be of childbearing potential unless they meet one of the following criteria:

- The patient has been postmenopausal (non-therapy-induced amenorrhea) for at least 12 continuous months with no other identified cause
- The patient had a surgical bilateral oophorectomy (with or without hysterectomy) more than 6 weeks prior to enrollment
- The patient had a hysterectomy

Female patients of reproductive or childbearing potential who are unwilling to use a method of contraception that results in a failure rate of <1% per year or remain abstinent (refrain from heterosexual intercourse) during the treatment period and for at least 60 days after the last dose of study drug will be excluded from study participation.

Abstinence is acceptable only if it is in line with the preferred and usual lifestyle of the patient. Periodic abstinence (e.g., calendar, ovulation, symptothermal, or postovulation methods) and withdrawal are not acceptable methods of contraception.

Examples of contraceptive methods with a failure rate of <1% per year include the following:

- Sterilization, bilateral surgical tubal ligation
- Intrauterine device
- Combined oral contraceptive pill*
- Contraceptive transdermal patch (estrogen and progestin containing)

Women using estrogen-containing hormonal contraceptives as a method of contraception must also use a barrier, such as a male condom, in conjunction with the hormonal contraceptives.

- Hormonal vaginal device
- Progestogen-only hormonal contraception associated with inhibition of ovulation
- Implants for contraception
- Injections for contraception (with prolonged release)

Sole sexual partner consisting of surgically sterilized male partner with appropriate
postsurgical verification of the absence of spermatozoa in the ejaculate. Patients
may provide verbal confirmation that the partner completed appropriate follow-up
after vasectomy. Sites are not required to obtain partner medical records.

For Men

All men must agree to remain abstinent (i.e., refrain from heterosexual intercourse) or use contraceptive measures and agreement to refrain from donating sperm, as defined below:

- With female partners of childbearing potential, men must remain abstinent or use a condom plus an additional contraceptive method that together result in a failure rate of <1% per year during the treatment period and for at least 120 days (4 months) after the last dose of study treatment. Men must refrain from donating sperm during this same period.
- With pregnant female partners, men must remain abstinent or use a condom during the treatment period and for at least 28 days after the last dose of study treatment to avoid exposing the fetus.

For Men and Women

The reliability of sexual abstinence should be evaluated in relation to the duration of the clinical trial and the preferred and usual lifestyle of the patient. Periodic abstinence (e.g., calendar, ovulation, symptothermal, and postovulation methods) and withdrawal are not acceptable methods of contraception.

Appendix 5 Health Assessment Questionnaire—Disability Index (HAQ-DI)

Name Date PATKEY#_ - -	Γ										
In this section we are interested in learning how your illness affects your ability to function in daily life. Please feel free to add any comments on the back of this page.											
Please check the response which best describes your usual abilities OVER THE PAST WEEK:											
Without With With UNABLE PMSVIS_ANY SOME MUCH To Do Difficulty Difficulty Difficulty RASTUDY_											
DRESSING & GROOMING QUESTNUI	vi										
Are you able to:											
- Dress yourself, including tying shoelaces and doingbuttons?	_										
- Shampoo your hair? DRESSNE											
ARISING											
Are you able to:											
- Stand up from a straight chair?											
- Get in and out of bed?											
EATING											
Are you able to:											
- Cut your meat?											
- Lift a full cup or glass to your mouth											
- Open a new milk carton?											
WALKING											
Are you able to:											
- Walk outdoors on flot ground?											
- Climb up_five taps? WALKNEW											
Please che k any AIDS OR DEVICES that you usually use for any of these activities:											
Cane Devices used for dressing (button hook, zipper pull, long-handled shoe horn, etc.)											
Walker Built up or special utensils											
Crutches Special or built up chair											
Wheelchair Other (Specify:) DRSGASS	Γ										
RISEASST_											
ĒATASST_											
Please check any categories for which you usually need HELP FROM ANOTHER PERSON:	Г										
Dressing and Grooming Eating											
Arising Walking											

@Stanford University

HAQ - United States/English HAQ-DI_AU1.0-eng-USori.doc

Please check the response which best describes your usual abilities OVER THE PAST WEEK: Without With With UNABLE SOME ANY MUCH To Do Difficulty **Difficulty Difficulty HYGIENE** Are you able to: - Wash and dry your body? - Take a tub bath? - Get on and off the toilet? HYGNNEW_ REACH REACHNEW 1 Are you able to: - Reach and get down a 5 pound object (such as a bag of sugar) from just above your head? - Bend down to pick up clothing from the floor? GRIP Are you able to: - Open car doors? - Open jars which have been previously opened? - Turn faucets on and off? **ACTIVITIES** Are you able to: - Run errands and shop? - Get in and out of a car? - Do chores such as vacuuming or ACTIVNEW_ Please check any AIDS OR DEVICES that you usually use for any of these activities: Bathtub bar Long-handled appliances for reach Long-handled appliances in bathroom Other (Specify: _ check any categories for which you usually need HELP FROM ANOTHER PERSON: HYGNASST Hygiene _Gripping and opening things RCHASST_ Reach Errands and chores GRIPASST_ ACTVASST_ We are also interested in learning whether or not you are affected by pain because of your illness. How much pain have you had because of your illness IN THE PAST WEEK: PLACE A VERTICAL (I) MARK ON THE LINE TO INDICATE THE SEVERITY OF THE PAIN. NO SEVERE PAIN PAIN PAINSCAL 100 Λ

HAQ - United States/English HAQ-DI_AU1.0-eng-USori.doc

Appendix 6 The Short-Form 36 Version 2 Health Survey (SF-36v2)

Your Health and Well-Being

This survey asks for your views about your health. This information will help keep track of how you feel and how well you are able to do your usual activities. Thank you for completing this survey!

For each of the following questions, please mark an \boxtimes in the one box that best describes your answer.

1. In general, would you say your health is:

2. Compared to one year ago, how would you rate your health in general now?

Much better	Somewhat	About the same as one year ago	Somewhat	Much worse
now than one	better		worse	now than one
year ago	now than one		now than one	year ago
	year ago	V	year ago	V

3.	The following questions are about activities you might do during a typical
	day. Does your health now limit you in these activities? If so, how much?

		Yes, limited a lot	Yes, limited a little	No, not limited at all
a	Vigorous activities , such as running, lifting heavy objects, participating in strenuous sports	1	2	3
b	Moderate activities, such as moving a table, pushing a vacuum cleaner, bowling, or playing golf	1	2	3
c	Lifting or carrying groceries	1	2	3
d	Climbing several flights of stairs	1	2	3
e	Climbing one flight of stairs	1	2	3
f	Bending, kneeling, or stooping	1	2	3
g	Walking more than a mile	1	2	3
h	Walking several hundred yards	1	2	3
i	Walking one hundred yards	1	2	3
	Bathing or dressing yourself	П,	\Box	П.

	following problems with y result of your physical he		or other re	gular daily	activities g	is a
		All of the time	Most of the time	Some of the time	A little of the time	None of the time
a	Cut down on the amount of time you spent on work or other activities	1	2	3	🗖 4	
b	Accomplished less than you would like	1	2	3	4	5
c	Were limited in the kind of work or other activities		2	3	4	5
đ	Had difficulty performing the work or other activities (for example, it took extra effort)	1	2	3	4	5
5.	During the past 4 weeks , following problems with y result of any emotional problems	your work	or other re	gular daily	activities a	as a
	Ship Ballana	All of the time	Most of the time	Some of the time	A little of the time	None of the time
a	Cut down on the amount of time you spent on work or other activities	1	2	3	4	
b	Accomplished less than you would like	1	2	3	4	5
c	Did work or other activities less carefully than usual	1	2	3	4	5

4. During the past 4 weeks, how much of the time have you had any of the

6.	emotional pr	the past 4 weeks , to what extent has your physical health or nal problems interfered with your normal social activities wife friends, neighbors, or groups?							
	Not at a	ll Slightly	Moderatel	y Quite a bit	Extremely				
	▼		3	▼	5				
7.	How much b	odily pain hav	e you had du	ring the past 4	weeks?				
	None	Very mild	Mild Mo	oderate Sever	re Very severe				
	_ ı	2	3		5 6				
8.	_	ast 4 weeks, he ling both work	700000		with your normal ework)?				
	Not at a	ll A little bi	t Moderatel	y Quite a bit	Extremely				
		2	3	. ↓	, s				

comes closest to the during the past 4 we	• •	een feeling	. How mu	ch of the tim	ie
	All of the time	Most of the time	Some of the time	A little of the time	None of the time
Did you feel full of life?	1	2	3	4	5
ь Have you been very nerv	7ous?	2	3		5
dumps that nothing could cheer you up?	1	2	3		5
d Have you felt calm and peaceful?		2	3	4	5
e Did you have a lot of end	ergy?	2	3	4	5
Have you felt downheart and depressed?	ed1	2	3	4	5
E Did you feel worn out?	1	2	3	4	5
h Have you been happy?		2	3	4	5
i Did you feel tired?		2	3	4	5
During the past 4 we emotional problems friends, relatives, etc	interfered with				
All of	Most of So		A little of the time	None of the time	
▼	▼	▼	▼	▼	

9. These questions are about how you feel and how things have been with you

 $SF-36v2^{\circ}$ Health Survey © 1992, 1996, 2000 Medical Outcomes Trust and QualityMetric Incorporated All rights reserved $SF-36^{\circ}$ is a registered trademark of Medical Outcomes Trust ($SF-36v2^{\circ}$ Health Survey Standard, United States (English))

11. How TRUE or FALSE is each of the following statements for you?

		Definitely true	Mostly true	Don't know	Mostly false	Definitely false
a	I seem to get sick a little easier than other people	1	2	3	4	5
b	I am as healthy as anybody I know	1	2	3	4	5
c	I expect my health to get worse	1	2	3		5
d	My health is excellent	1	2	а	4	5

Thank you for completing these questions!

